**Study Population:**

Describe the characteristics of the subject population, including age range, gender, ethnic background and health status. Identify the criteria for inclusion and exclusion.

Provide the following information:

- A description of the subject selection criteria and rationale for selection in terms of the scientific objectives and proposed study design;
- A compelling rationale for proposed exclusion of any sex/gender or racial/ethnic group;
- Justification for the inclusion of vulnerable groups such as children, prisoners, adults with impaired consent capacity, or others who may be vulnerable to coercion or undue influence.

Please consider these resources:

[NIH Diversity Policy](#)

[FDA Diversity Guidance](#) 

CARE2HOPE covers the following counties: Rowan, Bath, Morgan, Menifee, Elliott, Lee, Owsley, Wolfe, Perry, Letcher, Leslie, Knott. We will recruit participants at all seven jails serving the 12 CARE2HOPE counties; these jails are either located in our CARE2HOPE counties (N=5; Rowan, Lee, Perry, Leslie, Letcher), or our counties have contracts with them to incarcerate their residents (N=2; Montgomery, Clark). To be eligible to take part in Project START-C2H, an individual must:

EITHER:

- (1) be a participant in the CARE2HOPE longitudinal survey (IRB Protocol #43520) who consented to be contacted for future research; and
- (2) be a resident of or anticipate being released to one of the 12 CARE2HOPE counties randomized to intervention or control data collection; and
- (3) be incarcerated in a local jail and expected to be released in <21 days;

OR:

- (1) Be a resident of or anticipate being released to one of the 12 CARE2HOPE counties randomized to intervention or control data collection
- (2) Have used opioids to get high in the 30 days before they were incarcerated, or have injected any drug to get high during that period;
- (3) Be aged 18 or older
- (4) be incarcerated in a local jail and expected to be released in <21 days

We have the opportunity to offer the intervention to individuals enrolled in the comparison counties who have completed 3-month surveys, and feel that offering them this intervention is an ethical best practice. We are not proposing any additional quantitative data collection with them, but these individuals will be eligible for qualitative interviews as part of our continuous quality improvement component.

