#### COVID-19 Policies

We are changing the trial duration from three years to two years. To accommodate this shorter time period, we are modifying the study design from a stepped-wedge trial to a case crossover trial. We will randomize the 12 counties to two groups of six counties each versus three groups of four counties each. All counties will start at the same time. During months 1-6, counties randomized into Group 1 will receive the intervention, while counties randomized to Group 2 will serve as the comparison group. In Months 7-12, Group 1 counties will shift to the comparison group, and Group 2 counties will receive the intervention. In Months 13-18 we will conduct follow-up assessments in all counties. Months 19-24 will be devoted to data analysis and dissemination of the findings.

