##### d) Recruitment via existing study cohorts.

Study staff will contact participants enrolled in Kentucky CARE2HOPE (IRB # 43520), this protocol (CARE2HOPE UH3 Phase), and PROUD-R2, who gave their consent to be contacted about future studies. Note that PROUD-R2 is a collaborative project with Oregon Health and Science University (main site) and the Ohio State University and under the purview of the University of Utah IRB (IRB 00117831). We implemented IRB # 52430 in November 2019 randomizing the first four counties in the stepped-wedge design to the control group including Leslie, Letcher, Menifee, and Perry counties. These counties are randomized to the intervention group with the new study design. All participants currently enrolled will now be eligible for the intervention.

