laptop and access to the electronic screener during any recruitment event. Staff will then follow-up with the individuals to let them know if they are potentially eligible/not eligible; if eligible, staff will ask if the individual would like to complete the screener. Interested individuals may also complete the pre-screening survey themselves if preferred due to limited time, share with staff, who will then follow-up with them to let them know if they are potentially eligible/not eligible; if eligible, staff will ask if the individual would like to complete the screener. Staff will store completed paper screeners in a lock box and then in a locked filing cabinet in their field office upon return.

Once we enroll 15 individuals in a county, we will place a hold on additional recruitment efforts for that county; however, we will resume recruitment again when all intervention counties are switched to control and all control counties are switched to intervention per our study design (cross-over trial).

6/28/22 Modification - Study staff will contact participants currently enrolled in comparison counties and offer them enrollment in the intervention group.

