START core components: (1) Hold pre- and post-release program sessions with clients transitioning back to the community from a correctional setting; this component has been modified to include individuals who have been criminal justice involved in the last thirty days who are living in communities covered by our project; (2) Use a client-focused incremental risk reduction approach; (3) Use assessment & documentation tools to provide structure; (4) Hire program staff that are familiar with HIV/STIs/HCV prevention and with the specific needs of people being released; (5) Staff /client relationships must be maintained post-release; in the case of those individuals recruited from the community the relationship must be built and maintained in the community setting; (6) Conduct enrollment and schedule four intervention visits in the community over the span of 3 months that: a. give HIV/STI/HCV information; b. review client's HIV/STI/HCV risk; c. identify transitional needs; d. develop a personalized risk reduction and transitional plan; e. make facilitated referrals; (7) Schedule four post-release sessions, or for those enrolled in the community, post-enrollment sessions, to review and update the risk reduction/transitional plan(s) and provide facilitated referrals; (8) Provide fentanyl education, asking participants to watch a 4-minute educational video for FTS cited in previous research and available on YouTube at <https://www.youtube.com/watch?v=glovAAV-Amg>, assess fentanyl knowledge through a quiz (attached), and provide fentanyl test strips at the first post-release session or for those enrolled in the community, the first post-enrollment session; and, provide fentanyl test strips and condoms at each subsequent post-release session or for those enrolled in the community, post enrollment sessions; (9) Actively maintain contact with clients.

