#### Comparison Condition

We will initiate the comparison group in each county six months before the intervention begins. The current "treatment as usual" condition for most individuals, especially individuals not entering parole/probation supervision, is to provide no post-release services. Given the high risk of overdose post-release, we will conduct a pre-release overdose intervention with the comparison cohort. Individuals recruited in the community will receive overdose education during their baseline visit as well. Overdoses are not a primary study outcome, and it would be unethical to withhold overdose education from this cohort. Six months before the intervention starts in a county, REHNS will use the same pre-release recruitment, consent, and enrollment protocols (including eligibility criteria, except individuals must live in counties that are currently randomized to the comparison group) as proposed for the intervention condition. As with START's original evaluation, we will administer a single session, pre-release intervention for the comparison group; if someone is recruited in the community, they will receive this visit as well. Specifically, the comparison group participants will complete the a training with people demonstrating how to respond to an overdose and narration on preventing, recognizing, and responding effectively to an opioid OD, accompanied by information about Kentucky's Good Samaritan Law and Naloxone Access Law. REHNS will answer questions after the video. Individuals will receive a Community Resource Guide at this visit.

As in the intervention group, comparison group participants will complete assessments at pre-release (two sessions), for those recruited in the community this will happen at the REHNS office, and at 3 months and 6 months weeks post-release (post-enrollment for those recruited in the community). Surveys will be identical to those delivered to the intervention cohort, as will incentives. No interventions will be delivered at these follow up appointments. Retention efforts for comparison participants will be identical to those for intervention participants (described previously).

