- At the start of the session, the participant will confirm that they are in a confidential space, free of foot traffic and feel comfortable completing the interview. If these criteria are not met, study staff will end the session. The participant will be encouraged to follow-up with study staff once released from jail. If all criteria are met, prior to starting the interview, study staff will inform the participant how confidentiality will be protected via Zoom, for example, using UK Zoom, which is HIPPA compliant and that the waiting room will be enabled during the interview. There is a chance that jail staff could be close to the confidential space and potentially overhear so we cannot guarantee confidentiality completely.

Retention efforts are described in the data collection section. In addition to the locator form, we will also send reminder letters to study participants, reminding them about follow-up appointments or to contacts provided by study participants. Letters for phone calls due to COVID-19 and for normal operations are attached. We will distribute flyers in varied locations in the community as reminder that study participants are eligible for follow-up surveys as an additional strategy to ensure retention.

6/28/22 Modification: As noted in the data collection section, we will drop the 6-month follow-up surveys for newly recruited participants once approved by the IRB.

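### Does offering the intervention to comparison participants spoil the control arm, given that the SAP names no post visit and no coding rule for them?

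*Combined protocol and SAP*

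**What the plan says.** **Offer to comparison participants.** Under Study Population the protocol says: "We have the opportunity to offer the intervention to individuals enrolled in the comparison counties who have completed 3-month surveys". It adds: "We are not proposing any additional quantitative data collection with them". In the recruitment section, the note dated 6/28/22 reads: "Study staff will contact participants currently enrolled in comparison counties and offer them enrollment in the intervention group". That note gives no survey condition.

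**Follow-up.** The Comparison Condition section schedules assessments at 3 and 6 months and states: "No interventions will be delivered at these follow up appointments". The 6/28/22 modification in Research Procedures says: "we will drop the 6-month follow-up surveys for newly recruited participants once approved by the IRB". Data Collection repeats this. Participants already enrolled are not mentioned.

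**Design.** Counties swap conditions at mid-trial: "In Months 7-12, Group 1 counties will shift to the comparison group, and Group 2 counties will receive the intervention". For the four counties that began as controls in November 2019 under the stepped-wedge design, the protocol says: "All participants currently enrolled will now be eligible for the intervention". The START programme is to "schedule four intervention visits in the community over the span of 3 months".

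**Analysis.** The SAP's quantitative section fits a generalised linear mixed model with a pre-post indicator, an indicator for the intervention group and their product. The within-person covariance matrix is two by two, so each person contributes one pre and one post measure. The section does not name the post visit or define the group indicator for someone who changes condition. The Power section calls the analysis exploratory and sets alpha at 0.10.

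**The concern.** Three omissions seem to combine. First, the recruitment note, taken alone, would let staff treat a control before the 3-month survey. Second, even with the Study Population condition in force, a control enrolled before June 2022 could start the intervention between months 3 and 6 and still have a 6-month survey scheduled. Third, the SAP does not say which of the two surveys is the outcome, or that a control who is later treated stays in the control group.

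If treated controls were analysed as untreated, the time-by-intervention coefficient would be pulled towards zero. The SAP's triangulation section uses that test, at p < 0.10, as one of two inputs when it concludes benefit, harm or no effect, so a diluted null would carry some weight. The November 2019 controls raise a related question: one person might be enrolled under both conditions, and the documents do not say whether these people are in the analysis set.

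**Working it through.** **1. The plan's own figure.** Inputs from the SAP Power section: 12 counties, 20 participants each, ICC 0.05, within-person correlation 0.35, alpha 0.10, effect 0.55. Assumed here: two-sided test, unit SD, 6 counties against 6 (120 per arm), 12 − 2 = 10 degrees of freedom.

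- Variance of change: 2 × (1 − 0.35) = 1.30
- Design effect: 1 + 19 × 0.05 = 1.95
- SE = √(1.30 × 1.95 × 2/120) = 0.2055
- Noncentrality: 0.55/0.2055 = 2.68
- Power (noncentral t, 10 df) = 0.801, against 0.80 stated

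The power statement reproduces. It presumes one pre measure, one post measure and no exposed controls.

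**2. Which survey is post?** The model takes one post measure. The 6-month survey is dropped for new recruits, so only the 3-month survey exists by design for everyone. The Study Population section makes completion of that same survey the gate for the offer and proposes no further quantitative data collection afterwards. These facts point to 3 months.

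**3. Do the two statements of the offer conflict?** The Study Population section covers eligibility, and the recruitment note covers who makes contact. A contact line need not repeat an eligibility condition. Read together, contact goes to comparison participants and the offer goes to those past the 3-month survey.

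**4. Result on that reading.** The share of controls exposed before the post measure is u = 0. The effect stays at 0.55 and power at 0.80.

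**5. What if the reading is wrong?** With e the share of the full effect that exposed controls have gained, the expected contrast is 0.55 × (1 − u × e). The documents give neither u nor e, so these are illustrations.

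For e, assume the effect builds evenly over the 3-month programme and that controls enrolled evenly over time.

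- *6-month post, offer only after the 3-month survey.* Controls not yet at month 3 when the offer begins have 3 months of exposure before the 6-month survey. Those between months 3 and 6 average 1.5. The mean is (3 + 1.5)/2 = 2.25 months, so e = 2.25/3 = 0.75.
- *3-month post, recruitment note alone.* Mean exposure is 1.5 months, so e = 1.5/3 = 0.50.

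For u in the second case, assume control enrolment spread over 12 months before the offer. Then 3/12 = 25% of controls had not reached their 3-month survey. Acceptance of 20% or 50% gives u = 0.05 or 0.125.

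| Case | u | e | Contrast | Power |
|---|---|---|---|---|
| Natural reading | 0 | – | 0.550 | 0.801 |
| 6-month post | 0.10 | 0.75 | 0.509 | 0.745 |
| 6-month post | 0.25 | 0.75 | 0.447 | 0.648 |
| Note alone, 3-month post | 0.05 | 0.50 | 0.536 | 0.783 |
| Note alone, 3-month post | 0.125 | 0.50 | 0.516 | 0.755 |

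With e = 1, the 6-month rows fall to 0.724 and 0.589, but that requires every exposed control to have the full effect by the survey, which an average exposure of 2.25 months does not support. Even enrolment is itself doubtful, because the protocol holds recruitment in a county at 15 people and resumes at the switch. The model is also a parallel approximation to a county crossover: dropping the design effect raises baseline power to 0.966, so the size of any loss depends on the variant chosen.

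**The case for a change.** The strongest case for a change is that a reader cannot tell from the SAP which survey the interaction coefficient refers to, and that the Study Population section does not close the matter. It rules out additional data collection, but a 6-month survey already on the schedule for an earlier enrollee is arguably not additional. A 6-month outcome could then include treated controls coded as untreated, and it would be missing by design for later recruits, which an imputation plan written for non-response and attrition does not address. A few sentences would settle all of this without new data, and exploratory status does not excuse leaving an outcome undefined.

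The textual part stands: the post visit is unnamed, the coding rule is unwritten, the recruitment note omits the condition, and the status of the November 2019 controls is unstated. The inference to bias does not stand. It needs analysts to choose the one follow-up that part of the sample will never have, or staff to act on the recruitment note while ignoring the eligibility section. Coding people by the condition under which they enrolled is the ordinary default in a randomised comparison. The design figure and the 2023 modification memo are listed as attachments but cannot be seen here, and they may already state the timing.

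**Conclusion.** The gap is real, but it is one of missing detail that analysts would fill sensibly, so it calls for no change to the plan. If the offer follows the 3-month survey and that survey is the post measure, as the documents together suggest, the main contrast is clean and power stays at 0.80.

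What remains exposed is the set of 6-month surveys already scheduled for earlier comparison enrollees. The possible dilution there cannot be estimated from the documents. Power of about 0.75 with 10% of controls exposed, or 0.65 with 25%, is illustrative and rests on assumed uptake, even enrolment, an evenly building effect and the parallel 10-df approximation. No figure can be put on the November 2019 controls.

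The consequence is also limited by the plan. The analysis is declared exploratory, a conclusion of no effect requires the qualitative findings to agree, and divergent results are sent back to the data. The conclusion rests on two inferences, neither written outright: that the Study Population condition applies to the recruitment note, and that post means the 3-month survey.

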#### CQI

Pharmacists: Using the contact information from the program records, Graduate Research Assistants, Emory University, will invite the pharmacists trained by CARE2HOPE study on Vivitrol dispensing via e-mails and follow-up phone calls.

REHNs (research study staff): Graduate Research Assistants, Emory University, will invite the REHNs to take part via e-mail and follow-up phone calls. To avoid undue pressure, REHNs' decisions to enroll or refuse to participate will be kept confidential from the study leadership and management team (MPis [name] and [name], Project Director, [name] and Project Manager, [name]).

START-C2H participants: We will stratify the study roster from the REDCap database by county (n=12), then by gender (women and men), then by pharmacy-based Vivitrol participation status (Yes or No), resulting in 48 strata. Next, we will randomly select one participant from each stratum and will contact them using contact information from the study database. We will invite these individuals via phone; if a participant from a particular stratum refuses to participate, we will randomly select a replacement from the same stratum. Prior to the phone calls by the research assistants, our Re-entry Health Navigators (REHNs) will notify all eligible participants (i.e., those who participated in at least two START-C2H health linkage intervention sessions) about the forthcoming CQI interviews. This notification will be sent via text message to participants' phones using contact information from the study database or through Facebook Messenger (private CARE2HOPE account). This short notification will inform the participants that CARE2HOPE research assistants will call them to invite them for the interview and clarify that participation is voluntary. The notification text is provided as an attachment. Each REHN will provide their own phone numbers as part of the text.

#### COVID-19 Policies

We will use UK PR-approved flyers to recruit individuals from the community. We will post flyers in places where potentially eligible people may gather, including, but not limited to homeless shelters, grocery stores, Walmart stores, etc. We will also continue to work with jails, asking them to distribute flyers in the personal effects of individuals incarcerated. Individuals who are interested in learning more about the study can scan the QR code on the flyer to access an online eligibility survey through REDCap. If a potential participant is eligible, they will be asked to submit their contact information and the study team member will contact them. A copy of the survey is attached. UK-PR approved flyers including one for the community in general and one specifically for probation, parole, and pre-trial services are attached. We will provide business cards to Syringe Service Programs and other agencies as requested to enclose with packets provided to their clients. Given the volume of potential clients, it's more cost effective to print business cards than flyers for the packets. The content is the same as the UK PR and IRB-approved flyer with the exception of an additional number for screening. We are collaborating with the Department of Corrections to increase awareness about our study. DOC staff will provide a brief description about our study when they meet with a client in-person, via text or email messages, and through letters. CARE2HOPE study staff will provide the letters (printed on UK letterhead) and flyers in sealed envelopes to DOC staff who will then address the envelopes and send to potentially eligible clients. Scripts are provided for each of these strategies.

We will advertise the study on our CARE2HOPE facebook page using our approved community flyer. Additionally, we will promote the study through paid advertisement through Facebook Ads. Our approved flyer will be used for the ad and we will target our 12 study counties. We will advertise the study through radio ads in our study counties. We will also promote the study through newspaper ads, use a flyer that highlights key information about the intervention, use a flyer focusing on rural health issues, and use yard signs in varied locations. To enhance our retention efforts, we will use a flyer for reminding participants about follow-up appointments.

We will encourage participants to make referrals to the study. Participants will receive \$10 per eligible referral, up to three, for a total of \$30. We will ask study participants to give a coupon to each referral, allowing us to track the number of individuals who are eligible and ineligible. The coupon number is a unique alpha numeric code that study staff will assign and track through an excel file. The referral coupon is attached.

